- Overall study success criteria of at least a 30% difference between the test device group and the placebo group, comparing the proportion of individual successes in each group.
- It is anticipated that about 50% of subjects in the test device group and about 20% of subjects in the placebo group will meet the individual success criteria, and
- Intended application of a two-tailed test with an alpha value of 0.05 and Power of 0.8

- the sample size of 25 available subjects per group (test group and the control group, separately) has been determined using the following reference calculator: *Hypothesis Testing: Categorical Data - Estimation of Sample Size and Power for Comparing Two Binomial Proportions* in Bernard Rosner's *Fundamentals of Biostatistics*.

For the purposes of sample size calculation, a subject loss-to-follow-up of 20% is anticipated.

Therefore, a minimum starting sample size of 30 evaluable subjects in each group is needed to ensure that a sufficient number remains at the end of the trial (25 subjects per group) for any significant differences found between groups to be considered statistically valid and representative of the general population being sampled. This results in a total of 60 subjects being enrolled in this study across both study procedure groups.

RANDOMIZATION

Subject allocation to procedure group will be via variable block randomization with varying block sizes of two and four used at random to minimize the likelihood of predicting the next procedure group assignment. In addition, randomization will be stratified by Fitzpatrick Skin Type grouping

Randomization will be attained using computer generation sequence methodology, ensuring that the randomization methodology and the generated allocation sequence is concealed from the investigator and subjects.

Concealment will be insured as follows:

- Each computer-generated randomization sequence is unique and will therefore not be able to be replicated.
- Randomization will occur to either 'Test Group A' or 'B' rather than to a tests or placebo group, and only the study Sponsor will know which assignment corresponds to the active devices and which corresponds to the fake device. The Sponsor will not reveal this information to any source (investigators, subjects, or study Monitor) until the final study data analysis is complete.

TRIPLE BLIND DESIGN

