TABLE OF SUBJECT EVENTS

The following table provides a progressive summary of subject events throughout this study.

PRE-PROCEDURE ACTIVITIES	
1. A potentially well-suited and interested candidate for participation in the study attends the investigator's office.	
2. The investigator reviews the informed consent form with the candidate.	
3. If the candidate continues to be interested and voluntarily signs the informed consent form, the study qualification evaluation phase of the study is performed.	
4. A qualified subject is randomly assigned to procedure group.	
5. One-week individualized pain management regimen stabilization phase occurs	
6. The following measures are recorded during the Stabilization Phase: 
▪ Subject Daily Diary▪ Degree of Pain Ratings on final three days	
PRE-PROCEDURE ASSESSMENT PHASE	
CONTINUED STUDY ELIGIBILITY EVALUATION	

▪ Review of application of individualized pain management regimen throughout the Stabilization Phase▪ Evaluation of 3-day average VAS rating	
PRE-PROCEDURE MEASURES	

▪ Degree of Pain Rating▪ PRTEE, Grip Strength and TNFa measurements	
PRE-PROCEDURE VARIABLES	

▪ Baseline concomitant medication and treatment/therapy use	

- Historical pain medication and treatment/therapy use
- Baseline Lateral Epicondylitis pain variables
- Demographics

PROCEDURE ADMINISTRATION PHASE

Six 9-minute study procedure administrations with the Multi Radiance Medical® Prototype Device, two procedure administrations a week for three consecutive weeks administered at the test site.

PROCEDURE ADMINISTRATION PHASE MEASURES

DAILY THROUGHOUT THE THREE-WEEK PROCEDURE ADMINISTRATION PHASE

- Maintenance of the individualized pain management regimen, as needed
- Subject Daily Diary

WITHIN 24 HOURS OF COMPLETION OF THE FINAL PROCEDURE ADMINISTRATION

- Degree of Pain Rating
- PRTEE, Grip Strength and TNFa measurements
- Subject Satisfaction with Overall Outcome Rating
- Perceived Group Assignment
- Investigator Adverse Events Evaluation

POST-PROCEDURE ADMINISTRATION PHASE

DAILY THROUGHOUT THE ONE MONTH POST-PROCEDURE ADMINISTRATION PHASE

- Maintenance of the individualized pain management regimen, as needed
- Subject Daily Diary

ONE MONTH (30 DAYS) POST-PROCEDURE ADMINISTRATION PHASE (TEST SITE VISIT)

- Degree of Pain Rating
- PRTEE, Grip Strength and TNFa measurements

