The pre-procedure assessment phase will commence following successful completion of the individualized pain management regimen stabilization phase and just prior to commencement of the procedure administration phase.

CONTINUED STUDY ELIGIBILITY EVALUATION

Prior to the subject commencing the Pre-Procedure Assessment phase of the study, the investigator will:

- review the subject's recordings of use/application of his or her individualized pain management regimen to ensure it was correctly applied and recorded, and that there are no deviations significant enough to warrant withdrawal of the subject from the study prior to entry to the pre-procedure assessment phase; and
- calculate the average of the 3 VAS degree of pain scores recorded during the last three days of the individualized pain management regimen stabilization phase. In order for the subject to proceed, the 3-day average VAS score must be 50 or greater. If it is less than 50, the subject's participation in the study ends at this time.

PRE-PROCEDURE MEASURES

- Degree of Pain Rating. This will occur within 15 minutes prior to the initial procedure administration. The exact time the VAS rating is recorded will be noted.
- PRTEE, Grip Strength and TNFa measurements will be noted.

PRE-PROCEDURE VARIABLES

- Baseline concomitant medication and treatment/therapy use
- Historical pain medication and treatment/therapy use
- Baseline Lateral Epicondyle pain variables
- PRTEE, Grip Strength and TNFa measurements and Fitzpatrick Skin Type Classification will be noted.
- Demographics

PROCEDURE ADMINISTRATION PHASE

PROCEDURE ADMINISTRATION PROTOCOL

- The procedure administration phase of the study will commence within 15 minutes subsequent to completion of the pre-procedure assessment phase.
- The procedure administration phase comprises a total of six procedure administrations with the Multi Radiance Medical® MR5® Prototype Device: two

procedures a week for three consecutive weeks*, each procedure administration three to four days apart.

[figure not shown]
- *Three weeks, 2 times a week... Follow-up at 4th week after administration phase*

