 - In performing these evaluations, the numerical design and analysis of the blinding assessment will follow that outlined in Bang, et al. (Bang H, Ni L, Davis CE, Assessment of blinding in clinical trials. *Control Clin Trials*. 2004; 25:143-56)
- (v) **Qualitative analysis confirmation:** Evaluation of the comments provided by the subject, administration investigators and assessment investigators in the rationale section to explain the guess at group alignment will be evaluated and interpreted as follows to either support or negate the numerical findings:
 - *Positive blinding efficacy* will be supported through qualitative assessment of comments provided to support perceived group assignment that pertain to the determination being made based on treatment efficacy or lack thereof; e.g.: 'I can move my head from side to side easily and without it hurting and I couldn't do that before, so I believe I got the real treatment' or 'I haven't noticed any change in my Lateral Epicondyle pain, so I believe I got the fake treatment.'
 - *Blinding will be determined to have failed* if comments provided to support perceived group assignment pertain to factors such as sensation/visual clues, such as 'I saw/didn't see a light go on', or other factors that pertain to blinding having been compromised such as 'I overheard the doctor saying I wasn't getting the real treatment.'

Sample stratification distribution plan

Sample Stratification

In order to account for the possibility that skin phototype could affect the absorption of the energy emitted from the study device, and to ensure that the study sample is representative of the range of skin phototypes in the intended U.S. clinical patient population, recruitment and enrollment of the final 50 study subjects will be further stratified by Fitzpatrick skin type, as determined according to race, according to the process of proportionate allocation using a sampling fraction in each of the strata that is proportional to that of the total sample population.

According to the United States Census Bureau (www.census.gov), the distribution of race throughout the United States population as of 2014 is as follows:

- White (not Hispanic/Latino): 62%
- Hispanic/Latino: 17%
- African American: 13%
- Asian: 5%
- Other (including Hawaiian/Pacific Islander, America Indian, Alaskan and 2+ races): 3%

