Applying stratification according to the process of proportionate allocation using a sampling fraction in each of the strata that is proportional to that of the total sample population, the following formula is applied:

$$X = x1*X + x2*X + x3*X + x4*X + x5*X; \text{ where}$$

- X = Total Sample Population = 50 subjects
- x1 = Subpopulation: White = 0.62; $0.62*50 = 31$ subjects
- x2 = Subpopulation: Hispanic/Latino = 0.17; $0.17*50 = 8.5$ subjects
- x3 = Subpopulation: African American = 0.13; $0.13*50 = 6.5$ subjects
- x4 = Subpopulation: Asian = 0.05; $0.05*50 = 2.5$ subjects
- x5 = Subpopulation: Other = 0.03; $0.03*50 = 1.5$ subjects

Furthermore, in the following reference ...

Sauer's Manual of Skin Disease; Brian J Hall, John C. Hall; 2012

Chapter 35: Skin Disease in Ethnic Skin; [name] & [name] ... Fitzpatrick Skin Type is associated with race, as follows:

- "White": (Not Hispanic/Latino): Fitzpatrick Skin Types I, II & III
- "Ethnic" (Hispanic/Latino; African American, Asian): Fitzpatrick Skin Types IV, V & VI

In consideration of the distribution of race in the U.S population as determined above, this results in the need to recruit:

Ø 31 subjects with Fitzpatrick Skin Type I, II or III

Ø 19 subjects with Fitzpatrick Skin Type IV, V or VI (17 Hispanic/Latino+13 African American+5 Asian+3 'Other')

For ease and uniformity of randomization, given that there will be three test sites, and two procedure administration groups the sampling plan is rounded to even numbers within individual groups, as follows:

Test Site #1		
	Skin Type I, II & III	Skin Type IV, V & VI
Test Group	7	5
Placebo Group	8	4

Test Site #2		
	Skin Type I, II & III	Skin Type IV, V & VI
Test Group	4	3
Placebo Group	4	3

Test Site #3		
	Skin Type I, II & III	Skin Type IV, V & VI
Test Group	4	2
Placebo Group	4	2

While every effort will be made to recruit subjects evenly across the range of Fitzpatrick Skin Types within each of the two categories, it is anticipated that the majority of recruited Skin Types will fall within the range of II to V, inclusive, proportionate within the respective categories, as Fitzpatrick Skin Types I and VI are the least predominant Skin Types amongst the U.S. population.

Once a Fitzpatrick Skin Type category has been filled at a test site, no additional subjects will be enrolled in that category at that site.

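### The plan enrols 60 subjects, but the skin-type table and its closing rule stop enrolment at 50, which removes the dropout allowance

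*Combined protocol and SAP*

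**What the plan says.** Under *Rationale for sample size*, the plan asks for 25 subjects per group at the end of the trial, expects 20% loss to follow-up, and concludes that "a minimum starting sample size of 30 evaluable subjects in each group is needed". It adds: "This results in a total of 60 subjects being enrolled in this study across both study procedure groups". The *Sample size* paragraph just before it describes the 60 as evaluated for eligibility, but splits them 30 active and 30 placebo.

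Under *Sample stratification distribution plan*, the base is different: "recruitment and enrollment of the final 50 study subjects will be further stratified by Fitzpatrick skin type". The allocation formula uses "X = Total Sample Population = 50 subjects". After applying the census proportions, the plan says "this results in the need to recruit" 31 subjects of skin types I–III and 19 of types IV–VI. A table then divides these by site, arm and skin-type group. Its closing rule reads: "Once a Fitzpatrick Skin Type category has been filled at a test site, no additional subjects will be enrolled in that category" at that site.

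Three other provisions bear on what uses up a slot:

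- *Table of Subject Events* places randomization before the one-week stabilization phase: "A qualified subject is randomly assigned to procedure group".
- *Continued Study Eligibility Evaluation* then applies a further screen: "In order for the subject to proceed, the 3-day average VAS score must be 50 or greater". A subject below that value leaves the study.
- The ITT definition under *Primary Efficacy Outcome Statistical Evaluation Methods* includes only subjects who received at least the first procedure.

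**The concern.** The two sections give sites different stopping points, 60 enrolled or 50 enrolled. The table covers all three sites and both skin-type groups, so every possible subject falls in a capped category. When all six site-by-type categories are full, nobody else can be enrolled, and the 10 subjects added to absorb dropout have no slot.

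The plan never says whether a category is filled by subjects enrolled, randomized, treated or completed. This matters because randomization comes before the stabilization week. A subject who is randomized and then fails the 3-day VAS check has used an enrolment slot but is outside the ITT set. Imputation cannot bring that subject back, and no provision lets another take the place. At stake are the size of the primary analysis set and its power.

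**Working it through.** **1. The plan's enrolment figure.** Inputs from *Rationale for sample size*: 25 per group needed, 20% loss.

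25 × 1.20 = 30 per group, so 60 in total. This reproduces the plan's figure. Applying 20% loss to 30 leaves 30 × 0.80 = 24 per group, one short of the 25 intended; 25 / 0.80 = 31.25 would round up to 32.

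**2. The stratification table.** Cells are types I–III / IV–VI.

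| Site | Test | Placebo | Site total |
|---|---|---|---|
| 1 | 7 / 5 | 8 / 4 | 24 |
| 2 | 4 / 3 | 4 / 3 | 14 |
| 3 | 4 / 2 | 4 / 2 | 12 |
| All | 15 / 10 = 25 | 16 / 9 = 25 | 50 |

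Types I–III: 7+8+4+4+4+4 = 31. Types IV–VI: 5+4+3+3+2+2 = 19. Both match the plan's stated recruitment numbers.

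**3. The gap.** 60 − 50 = 10 subjects, 5 per arm; 10/60 = 17%. This equals the allowance, 2 × (30 − 25) = 10.

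**4. What remains after 20% loss.** 60 enrolled: 48, or 24 per arm. 50 enrolled: 50 × 0.80 = 40, or 20 per arm.

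**5. Power.** Inputs from the plan: response 50% v 20%, two-sided alpha 0.05, Fisher's exact test. For n per arm, power is the sum, over all pairs of responder counts (a, b) with two-sided Fisher p ≤ 0.05, of Bin(a; n, 0.5) × Bin(b; n, 0.2).

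| n per arm | Exact power |
|---|---|
| 20 | 0.409 |
| 24 | 0.493 |
| 25 | 0.510 |
| 30 | 0.596 |

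Like for like:

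- Completers after 20% loss: 24 v 20 per arm, 0.493 − 0.409 = 0.083 (from unrounded values).
- Every enrolled subject analysed: 30 v 25 per arm, 0.596 − 0.510 = 0.086.

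**6. Where the ITT set falls.** Let f be the share of the 20% loss that occurs before the first procedure. ITT size per arm is 30(1 − 0.2f) with 60 enrolled and 25(1 − 0.2f) with 50 enrolled. The plan does not give f. At f = 0 the sizes are 30 and 25; at f = 1 they are 24 and 20. The two comparisons in step 5 are therefore the ends of the range.

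**7. A table for 60.** Multiply the site-by-type totals by 60/50 = 1.2:

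- Site 1: 15/9 becomes 18/10.8
- Site 2: 8/6 becomes 9.6/7.2
- Site 3: 8/4 becomes 9.6/4.8

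Rounding to 18/11, 10/7 and 9/5 gives 37/23. At the plan's 62%/38% split, the targets are 0.62 × 60 = 37.2 and 0.38 × 60 = 22.8.

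**The case against.** The best defence is that the 50 are completers. The rationale wants 25 per group left at the end, and the table is exactly 25 + 25. If the table counts those who remain, the two sections agree and only a definition is missing. The authors may have meant this. But the stratification text speaks of recruitment, enrolment and the need to recruit, never ties a filled category to completion, and gives no way to reopen a slot. Even on this reading, a site with 15 type I–III subjects enrolled and not yet finished could not tell whether to take a sixteenth.

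The phrase about the final 50 could also mean the last 50 of 60 to be enrolled. The formula rules that out, because it makes 50 the total sample.

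The wording about evaluation for eligibility might make 60 a screening count. Screened-only subjects have no arm, however, and the plan splits the 60 by arm and calls them enrolled.

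Two points on size stand. The power loss arises only if sites obey the closing rule literally. Most of the shortfall against the planned 80% is also not due to this rule: even 30 per arm fully analysed gives 60%, because 25 per group is too few for the stated inputs. That is a separate matter. Imputation under ITT does keep losses after the first procedure, but not those before it.

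On the remedy, the cells for 60 are one reasonable rounding and not the only one. Some caps are odd, as some are in the present table.

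**Conclusion.** The concern holds, and the plan should be corrected. As written, the stratification section closes enrolment at 50 while the sample size section requires 60, and the missing 10 are the entire allowance for loss. If sites follow the closing rule, exact power at 50% v 20% drops by about 8 to 9 points: 60% to 51% with everyone analysed, or 49% to 41% among completers after 20% loss. The ITT analysis lies between these cases.

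These figures assume the plan's own response rates and 20% loss spread equally over the arms. They describe only the effect of the cap and take no account of any other weakness in the sample size calculation. That the table sums to 50 and the enrolment target is 60 depends on no assumption.

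**What to change.** Choose one of two options and state it.

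**A. Rebuild the table for 60.** Apply the closing rule to the site-by-type caps and say that a category is filled by randomized subjects. One workable set (types I–III / IV–VI):

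| Site | Cap | Test target | Placebo target |
|---|---|---|---|
| 1 | 18 / 11 | 9 / 6 | 9 / 5 |
| 2 | 10 / 7 | 5 / 3 | 5 / 4 |
| 3 | 9 / 5 | 4 / 3 | 5 / 2 |
| All | 37 / 23 | 30 | 30 |

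The arm columns are targets; the caps are what close enrolment.

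**B. Keep the 50-subject table as a completer target.** Define a filled category by subjects with the primary endpoint recorded, and state that replacements are allowed up to 60 enrolled in total.

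Under either option, state that 60 enrolled with 20% loss leaves 24 per arm, not 25. Under B, this means the 50-completer target is not expected to be fully met at that loss rate. Also change the *Sample size* paragraph to say that 60 subjects will be randomized; its 30 + 30 split shows that the present wording is only loose.

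The cost is one revised table or one definition, plus small wording changes. No subjects are added beyond the 60 already planned.

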CHANGE IN SUBJECT SELF-REPORTED VAS PAIN RATING FROM BASELINE TO STUDY ENDPOINT

Primary efficacy outcome measure for this clinical study will be a statistically significant difference in the proportion of subjects between test and control groups who achieve a clinically meaningful and statistically significant decrease in self-reported VAS pain rating from baseline to study endpoint.

Subjects meeting Individual Success Criteria

The individual subject success criteria is defined as a 30% or greater decrease in self-reported VAS pain rating at study endpoint relative to baseline.

Overall Study Success Criteria.

Overall study success criteria is defined as at least a 30% difference between procedure groups, comparing the proportion of individual successes in each group. It is anticipated that about 50% of subjects in the test group will meet the individual success criteria and about 20% of subjects in the control group will meet the individual success criteria.

Evaluation Time Points

The study end evaluation time point at which study success will be analyzed is within 24 hours following completion of the three-week procedure administration phase with the Multi Radiance Medical® MR5® Prototype Device. Study success will be evaluated at endpoint relative to baseline.

Hypotheses

- *Null Hypothesis:* There will be no statistically significant difference in the proportion of individual successes, as defined, between the test and control groups.

- *Alternative Hypothesis:* There will be a statistically significant difference in the proportion of individual successes, as defined, between the test and control groups, to the effect of 30% or greater.

PRIMARY EFFICACY OUTCOME STATISTICAL EVALUATION METHODS

Intent to Treat (ITT) Principle: Primary efficacy analysis will be according to the intent to treat (ITT) principle; wherein subjects will be included in the analysis if they were randomized to study procedure group, had a valid baseline (pre-procedure) visit including the required Lateral Epicondylitis pain VAS recordings; and received at least the first study procedure administration.

Missing data will be handled through all of the following methods:

- *Last Observation Carried Forward (LOCF):* by carrying forward the last recorded observation to fill in the subsequent missing value.

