- *Tipping Point Analysis:* Tipping point analysis will be used to examine the impact of missing data on the study conclusion. Tipping point analysis is defined as the difference in means (for continuous data) or the difference in the number of events (for binary data) between treatment groups in the missing cohort at which the study conclusion is changed. A tipping point analysis replaces the missing value with other values so that the resulting p-value is equal to the pre-specified significance level (i.e. $\alpha=0.05$, 2-sided).
- *Multiple Imputation Analysis:* Multiple imputation analysis is a strategy to handle missing values in a clinical trials wherein each missing value is replaced with a set of plausible values that represent the uncertainty about the right value to impute. Multiple imputation does not attempt to estimate each missing value through simulated values, but rather to represent a random sample of the missing values. This process results in valid statistical inferences that properly reflect the uncertainty that results from missing values, such as valid confidence intervals for parameters.

Multiple imputation inference involves three distinct phases:

1. The missing data are filled in m times to generate m complete data sets.
2. The m complete data sets are analyzed by using standard statistical procedures.
3. The results from the m complete data sets are combined for the inference.

Multiple imputation usually assumes that the data are missing at random (MAR). That is, for a variable Y , the probability that an observation is missing depends only on the observed values of other variables, not on the unobserved values of Y .

Pre-Protocol Analysis will also be performed for the set of all subjects who were randomized to procedure group and completed the study according to the full protocol.

Primary analysis of efficacy will be according to intent to treat (ITT) analysis through the application of:

- 1) **Fisher's exact test** to compare the proportion of success between the test and the control groups, considering that randomization has been diligently conducted and important covariates between the two groups are well balanced.

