2) **Parametric ANCOVA model** analysis with the mean change from baseline to study endpoint in Lateral Epicondyle pain ratings on the VAS as the dependent variable, procedure group as the independent variable of interest and baseline average Lateral Epicondyle pain VAS rating as a covariate. A two-tailed significance level of 5% will be considered to be statistically significant.

Covariates: The following potential covariate baseline variables will be adjusted, as applicable, through application of an ANCOVA analysis for the continuous variables and linear regression analysis for categorical variables.

- Baseline Lateral Epicondyle pain VAS rating
- Fitzpatrick Skin Type Classification
- Age
- Gender
- Demographics

SUPPORTIVE OUTCOME MEASURES

The following supportive outcome measures will be evaluated:

- a. Mean and individual subject changes in Degree of Pain VAS ratings across and between all study evaluation time points, within and between procedure groups
- b. Mean and individual subject changes in each of the PRTEE, grip strength and TNFa levels measurements across and between all evaluation points, within and between procedure groups
- c. Differences in satisfaction with Study Outcome Ratings between procedure groups at both evaluated time points, and any change between

SUPPORTIVE MEASURES STATISTICAL EVALUATION METHODS

- a. Supportive measures that are continuous variables will be analyzed through parametric analysis using ANCOVA. A two-way significance level of 5% will be statistically significant.
- b. Supportive measures that are categorical will be evaluated through linear regression analysis.
- c. Satisfaction with Study Outcome Ratings: will be tabulated according to category and reported as percentages. Satisfaction levels will be correlated with subject individual study success and recorded changes in Lateral Epicondyle pain VAS ratings from baseline to endpoint evaluations.

STATISTICAL EVALUATION OF APPLICATION OF PAIN MANAGEMENT REGIMEN

The impact of pain management regimen use on the study outcome measure will be evaluated through application of the following analyses:

- a. **Fisher's exact test** to compare the proportion of subjects requiring use of his or her individualized pain management regimen between the test and the control groups.

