FITZPATRICK SKIN TYPE CLASSIFICATION SCALE: The Fitzpatrick Skin Type Classification Scale is a numerical classification schema for human skin color developed in 1975 by Harvard Medical School dermatologist, [name], PhD. The scale classifies a person's complexion and their tolerance of sunlight.

The Fitzpatrick Classification Scale classifies skin type from I through VI according to the applicable criteria contained in the chart below.

Skin Type	Skin Color	Characteristics
I	White; very fair; red or blond hair; blue eyes; freckles	Always burns, never tans
II	White; fair; red or blond hair; blue, hazel, or green eyes	Usually burns, tans with difficulty
III	Cream white; fair with any eye or hair color; very common	Sometimes mild burn, gradually tans
IV	Brown; typical Mediterranean Caucasian skin	Rarely burns, tans with ease
V	Dark Brown; mid-eastern skin types	Very rarely burns, tans very easily
VI	Black	Never burns, tans very easily

POOLABILITY EVALUATION

The primary efficacy outcome is a binary variable, with success defined as a 30% or greater reduction in self-reported Degree of Pain rating on the 0-100 VAS from baseline to study endpoint evaluation. Poolability analysis for this primary binary outcome will be via the Breslow-Day test for homogeneity of odds ratios.

Furthermore, poolability analysis will also be conducted for the continuous outcome of mean change from baseline to study endpoint in self-reported Degree of Pain ratings on the 0-100 VAS through a treatment-by-subgroup interaction term applying a logistic regression model that also includes the main effect terms of all treatment groups.

SAFETY ANALYSES

Safety analyses will be based on all subjects who were randomized to the test or to the placebo procedure group. Safety will be assessed by evaluating and comparing frequency and incidence of observed and/or reported adverse events between test and placebo procedure groups. A chi-square test with a continuity correction will be performed to compare the percentage of subjects who had adverse events between test and placebo group subjects.

CASE REPORT FORMS

The case report forms that will be used to collect the data from each subject in this clinical study can be found in **Appendix E**.

REFERENCES

ⁱ Bocock MG, Collier JM, McNair PJ, Simmonds M, Larmer PJ, Armstrong B. A framework for the classification and diagnosis of work-related upper extremity conditions: systematic review. *Semin Arthritis Rheum*. 2009;38:296-311.

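### The poolability check for VAS change applies logistic regression to a continuous outcome, so it cannot be run as written, and its subgroup is not named

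*Combined protocol and SAP*

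**What the plan says.** The Poolability Evaluation section has two parts. For the responder endpoint it uses the Breslow-Day test. For VAS change it states that "poolability analysis will also be conducted for the continuous outcome of mean change from baseline to study endpoint", by means of a "treatment-by-subgroup interaction term applying a logistic regression model that also includes the main effect terms of all treatment groups". The section does not name the subgroup in either part. There are two candidates. One is site, since the sample stratification plan is drawn up "given that there will be three test sites, and two procedure administration groups". The other is skin type, since the Randomization section says that "randomization will be stratified by Fitzpatrick Skin Type grouping". The stated reason for attending to skin type is "In order to account for the possibility that skin phototype could affect the absorption of the energy emitted from the study device".

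For the responder endpoint itself, the primary efficacy methods specify an unstratified Fisher's exact test, "considering that randomization has been diligently conducted and important covariates between the two groups are well balanced". The Covariates paragraph that follows lists baseline VAS, Fitzpatrick type, age, gender and demographics. It says that these "will be adjusted, as applicable, through application of an ANCOVA analysis for the continuous variables and linear regression analysis for categorical variables". It does not say which outcome each adjustment applies to.

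**The concern.** A logistic model describes the probability of a binary event and has no meaning for a change score in millimetres. The same section treats the binary endpoint separately, so the sentence cannot be read as a second reference to responders. Cutting VAS change into two categories would only produce another binary check. An analyst must therefore replace the model. If the replacement is not fixed in advance, it will be chosen with data in hand.

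The likeliest quick repair is to change one word and keep the listed terms: treatment main effects plus a treatment-by-subgroup product. Depending on coding, that product can absorb ordinary differences between sites that are equal in both arms. The result could then be read as evidence that the sites should not be pooled. For a three-site study meant to support a marketing submission, this check is part of the case for pooling.

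**Working it through.** **1. Does the stated model run?** A logit fit to simulated continuous VAS change stops with an error that the outcome must lie between 0 and 1.

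**2. Layout.** The site tables in the sample stratification plan give test arm 12 + 7 + 6 = 25 and placebo arm 12 + 7 + 6 = 25. Types I–III sum to 7+8+4+4+4+4 = 31 and types IV–VI to 5+4+3+3+2+2 = 19. Both match the plan's own targets. The plan gives no operating figure for the poolability check to reproduce.

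**3. Assumptions, because the documents give none.** Residual SD σ is 20, 25 or 30 mm, with the baseline VAS covariate absorbed in it. Site 1 differs from sites 2 and 3 by d = 10 or 20 mm, equally in both arms. There is no true interaction, so a 5% test should reject in 5% of trials.

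**4. Linear model without a site main effect.** In each arm the between-site sum of squares is (12 × 13 / 25)d² = 6.24d². Put λ = 6.24d²/σ². At σ = 25, λ = 0.998 for d = 10 and 3.994 for d = 20.

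- 0/1 dummy coding: the numerator (2 df) has non-centrality λ from the active arm. The residual (46 df) has non-centrality λ from the placebo arm.
- Site-within-arm test: F on 4 and 44 df, with non-centrality 2λ.
- +1/−1 arm coding: because the arms are equal within each site, the product terms are orthogonal to the omitted site effect. The numerator (2 df) is central and the residual (46 df) has non-centrality 2λ.
- Site main effect included: F on 2 and 44 df, central, so 5%.

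| False significance | d = 10, σ = 25 (σ 30 to 20) | d = 20, σ = 25 (σ 30 to 20) |
|---|---|---|
| 0/1 dummy, 2 df | 12.1% (9.9–16.4%) | 35.1% (25.8–50.5%) |
| Site within arm, 4 df | 15.7% (12.1–23.0%) | 55.2% (39.5–77.1%) |
| +1/−1 arm coding | 4.4% (about 4.1–4.6%) | 3.1% (about 2.3–3.6%) |
| Site main effect included | 5.0% | 5.0% |

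**5. Power of the corrected interaction test.** Suppose the treatment effect at site 1 differs by 20 mm from that at the other sites. The site differences have weights n/2 = 6, 3.5 and 3, so the non-centrality is (6 × 6.5 / 12.5) × 20²/σ² = 3.12 × 400/625 = 2.0 at σ = 25. Power is 21.3%, and 15.9% to 31.3% for σ from 30 to 20. For skin type, the variance factor is 1/15 + 1/10 + 1/16 + 1/9 = 0.340. An interaction of 0.8 SD (20 mm at σ = 25) then has about 28% power.

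**6. What a stratified responder analysis would add.** All tables were enumerated at 50% versus 20%. The strata at 25 per arm come from the plan (test 15/10, placebo 16/9). Those at 30 per arm are scaled by assumption (18/12, 19/11). Skin type is taken as not prognostic.

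| Power | 25 per arm | 30 per arm |
|---|---|---|
| Fisher | 51.0% | 59.6% |
| Unstratified chi-square | 63.8% | 69.2% |
| Cochran-Mantel-Haenszel (CMH) by skin type | 62.5% | 69.4% |

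Stratifying itself adds 62.5 − 63.8 = −1.3 points, or 69.4 − 69.2 = +0.2 from the rounded figures (+0.1 unrounded). The rest of the gap to Fisher is Fisher's conservatism (size 2.2% at a 20% null rate). The plan also says "Overall study success criteria is defined as at least a 30% difference between procedure groups". If that rule applies to the observed difference, the chance of meeting both conditions is 50.5% and 56.1% under either test. The largest difference that is CMH-significant but not Fisher-significant is 28.0 and 26.7 points, below 30 in both cases.

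**The case against.** The defence has four good points.

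First, the sentence says the model includes treatment main effects, not that it includes nothing else. The missing subgroup term is partly an inference from loose wording. A reader might infer that this omission also stops the model running. It does not: only the mismatch between logistic regression and a continuous outcome does that.

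Second, the inflation is not universal. With +1/−1 arm coding on this balanced layout, the test without a site main effect is slightly conservative. A reader who infers that a linear version of the sentence must produce false interactions goes too far. What stands is that the plan fixes no coding, and the answer ranges from about 2% to 77% depending on that choice and on the assumed SD and site gap.

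Third, the affected check is an additional one. No rule says that a significant interaction blocks pooling or changes the primary conclusion, and the mismatch does not touch the Breslow-Day test. This limits the consequence. The sentence still cannot be executed, and no other section repairs it. The ANCOVA under the primary efficacy methods contains no interaction term.

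Fourth, it is tempting to infer that the primary responder test is defective because it ignores the randomisation strata. The documents do not support that. Unstratified Fisher is prespecified, valid and conservative, and the Covariates paragraph already lists Fitzpatrick type. The remaining gap is narrow: the methods named there, ANCOVA and linear regression, do not suit a binary endpoint.

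**Conclusion.** The poolability model for VAS change is wrong as written and should be corrected. The error is plain on the face of the section and rests on no assumption. The undefined subgroup is a second gap in the same sentence.

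The warning against changing only the word logistic does rest on assumptions: SD 20–30 mm, site gaps of 10 or 20 mm, and the planned layout. It holds for some codings and not for others. Including the subgroup main effect removes the dependence altogether.

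Neither the primary test nor the trial's conclusion is put in doubt. A supportive stratified responder analysis would be a useful option, not the repair of an error. Its benefit is a prespecified estimate by the randomisation strata, not more power from stratifying or a better chance of study success.

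**What to change.** Before unblinding, amend the Poolability Evaluation section:

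- Replace the logistic model for VAS change with a linear ANCOVA containing baseline VAS, arm, the named subgroup and the arm-by-subgroup interaction. Run it once with site and once with skin-type group (I–III versus IV–VI). Name the strata for the Breslow-Day test as well.
- Report site-specific and skin-type-specific treatment differences with 95% confidence intervals. At about 21% power, a non-significant site interaction is weak evidence that pooling is safe.

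Optionally:

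- Keep Fisher's exact test as the primary responder test and add one supportive analysis by the two skin-type strata, for example CMH without continuity correction plus a common effect estimate. CMH is asymptotic (size 5.1% at 25 per arm and a 20% null rate), which is a reason to keep it supportive. Do not cross skin type with site: those cells fall to 2 per arm.
- State in the Covariates paragraph which outcome each adjustment applies to.

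The cost is wording and a little extra analysis. No subjects, visits or new data are needed.
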